Deceased solid organ donors with hepatitis C virus (HCV) infection represent another potential source of expanding the organ donor pool. HCV affects about 1.6% of the general population in the United States. The prevalence of HCV was more than triple this number for American organ donors from 2004 - 2008 (Armstrong). Among high-risk donors, who represent up to 30% of all donors, the prevalence was as high as 18.2% (Ellingson, (Kucirka Am J Transplant 2009 PMID 20353475). Perhaps reflecting the ongoing opioid crises in the United States, in some organ procurement organization areas, nearly 15% of even the current general organ donor pool is HCV positive (personal communication, [name], CEO, New England Organ Bank). As these donors are typically young, the organs may be higher quality than would be otherwise available from HCV negative donors.

Historically, organs from HCV-positive donors have been underutilized. Reese, et al. identified 3273 HCV-antibody positive deceased kidney donors from 2005-2014 for whom organ donation was authorized (Reese). Only 2402/6546 (37%) of the donated kidneys were transplanted; 91% of the recipients had documented HCV infection. The other kidneys were discarded. In addition, as many as one third of solid organs may not be procured from potential donors who were HCV-antibody positive (Seem), presumably due to concerns they would not be utilized by any transplant center.

In the past, this hesitancy to use HCV-positive organs reflected concerns about the negative liver and extrahepatic outcomes of refractory HCV infection in the setting of immunosuppression. Still, many centers in the United States have utilized hepatitis C-positive solid organs for hepatitis C-positive recipients. For liver transplant, most studies have shown equivalent survival for those HCV-positive recipients who receive carefully selected HCV-positive livers, particularly if older donors (>55 years) and donor livers with fibrosis are avoided (Vargas, Marroquin, Berenguer). For kidney transplant, in one study the median waiting time for patients who accepted HCV-positive kidneys was 469 days versus 856 days for patients who received HCV-negative organs (Kucirka 20353475). In the era before direct acting antiviral agents (DAAs), the reduced mortality on the kidney wait list may have been offset by some increase in adverse post-transplant outcomes (Morales, Kucirka Am J Kid, Gasink, Fabrizi).

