Shorter wait time from listing to transplant is a potential benefit of accepting a HCV positive organ. To characterize wait time among HCV positive organ recipients, mean wait time in log₁₀ days will be calculated separately for liver and kidney transplant recipients. With a sample size of 10, 15, or 20 patients per HCV positive organ type and a standard deviation of 1 log₁₀ days of wait time, we have 80% power to obtain a two-sided 95% CI half-width of 8, 5, and 4 days, respectively (CI half-width of 0.9, 0.7, and 0.6 log₁₀ days).

To explore wait time by acceptance of HCV positive versus negative organs, wait time would be collected for the HCV positive organ recipient and the next HCV negative organ recipient at the transplant center, matched on blood type, gender, and transplant MELD (+/-5) for liver recipients and KDPI (+/- 0.25) for kidney recipients. Mean wait time in log₁₀ days for a HCV positive versus negative organ would be compared separately among liver and kidney recipients. We anticipate obtaining wait time on 60 transplant recipients (at least 20 liver and 20 kidney recipients). For a two-sided paired t-test assuming an alpha level of 0.05, we estimate having 80% power to detect a mean difference in wait time of 20, 10, and 8 days for sample sizes of 20, 30, and 40 patients, respectively.

Safety Analysis

Safety will be assessed during the study through the reporting of AEs and by clinical laboratory tests at various time points during the study. Concomitant medication usage will also be assessed throughout the study. Descriptive statistics on the number and types of AEs will be recorded and presented in a tabular format. Treatment-emergent AEs (TEAEs) will also be summarized by relationship to study drug and severity. In addition, TEAEs leading to premature discontinuation of the study drug will be summarized and listed. Liver or kidney grade 3 or 4 laboratory abnormalities will be described in the narrative.

Independent Data and Safety Monitor (IDSM)

An IDSM with relevant clinical expertise will be chosen who has no financial, scientific,

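### The wait-time precision and power figures rest on an unsourced SD of 1 log10 day, implausible for kidney if waits are roughly log-normal, and report fold ratios as days

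*Combined protocol and SAP*

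**What the plan says.** Under Statistical Considerations, Exploratory Endpoint, mean wait in log10 days is to be estimated separately for liver and kidney recipients. The planning inputs are put as "With a sample size of 10, 15, or 20 patients per HCV positive organ type and a standard deviation of 1", where the unit of that SD is the log10 day. From this the plan states: "we have 80% power to obtain a two-sided 95% CI half-width of 8, 5, and 4 days, respectively", and adds in parentheses a "CI half-width of 0.9, 0.7, and 0.6 log₁₀ days".

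The same section then matches each recipient to the next recipient of an HCV-negative organ at the center and compares mean log10 wait within organ type by a two-sided paired t-test (alpha 0.05, 80% power). The detectable effect is put as follows: "mean difference in wait time of 20, 10, and 8 days for sample sizes of 20, 30, and 40 patients, respectively". With matched pairs, those patient numbers are 10, 15 and 20 pairs. This sentence gives no SD, and no SD or correlation of the paired difference.

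The only numerical wait times in the documents are in Background and Scientific Rationale, for kidney, from one cited study: "the median waiting time for patients who accepted HCV-positive kidneys was 469 days versus 856 days for patients who received HCV-negative organs". No median or spread is given for liver.

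**The concern.** An SD of 1 on the log10 scale means a tenfold change per SD. That is a very wide spread to set beside a median of 469 days, and the plan neither sources it nor varies it. Half-widths and detectable differences on the log scale are proportional to the SD, so the value governs everything the section says the comparison can show.

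The units compound this. A difference in mean log10 days back-transforms to a ratio of geometric means, not to a number of days. A reader who takes 8, 5 and 4 days, or 20, 10 and 8 days, at face value would think the study can resolve waits to within a few days or weeks. At stake is what Objective 3 can conclude, since its hypothesis is that the wait is substantially shortened.

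**Working it through.** **Inputs.** From Exploratory Endpoint: SD 1 log10 day, n = 10/15/20 per organ, two-sided 95%, 80% power, 10/15/20 pairs. From Background: kidney medians of 469 and 856 days. Assumed, because the documents give nothing: log-normal waits, alternative SDs of 0.5 and 0.3, and within-pair correlation (rho) of 0 or 0.5.

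**1. Reproduce the half-widths.** With z(0.975) + z(0.80) = 1.960 + 0.842 = 2.80, the half-width is 2.80 × SD / √n. At SD 1 this is 0.886, 0.723 and 0.626, which round to the stated 0.9, 0.7 and 0.6. Antilogs of the rounded values are 10^0.9 = 7.9, 10^0.7 = 5.0 and 10^0.6 = 4.0: the stated 8, 5 and 4. (An exact t/chi-square half-width with 80% assurance is 0.834, 0.631 and 0.525, which matches only if rounded up.)

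**2. Reproduce the detectable differences.** The formula 2.80 × SD × √(2/pairs), with SD 1 and rho = 0, gives 1.253, 1.023 and 0.886. Rounded to 1.3, 1.0 and 0.9, the antilogs are 20, 10 and 8, as stated. Without the intermediate rounding they are 17.9, 10.5 and 7.7. An exact paired t-test gives 25.6, 12.6 and 8.6 with SD of difference √2, and 9.9, 6.0 and 4.6 with SD of difference 1; neither matches. The link to SD 1 is therefore inferred from the match, not stated in the plan.

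**3. Units.** Each figure is 10 raised to a log10 quantity, which is a ratio. Around 469 days, a half-width of 0.9 log10 runs from 469/7.94 = 59 days to 469 × 7.94 = 3,725 days. It is not 469 ± 8 days. This holds at any SD.

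**4. Plausibility of SD 1 for kidney.** If waits are log-normal with median 469 days, the 95% range is 469 × 10^(±1.96) = 5.1 to 42,773 days, or 117 years. The share above y years is 1 − Φ(log10(365.25y/469)): 28% above 5 years, 19% above 10 and 5.6% above 50.

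**5. What the design can detect.** The cited contrast is 856/469 = 1.83, or 0.261 log10. Detectable ratios use the formula in step 2. Power uses the exact paired t-test with SD of difference = SD × √(2(1 − rho)) and noncentrality 0.261 × √pairs / (SD of difference).

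| SD (log10) | 95% range around 469 days | Half-width as a factor, n = 10/15/20 | Detectable ratio, rho 0, 10/15/20 pairs | Power for 1.83-fold, rho 0 | Power for 1.83-fold, rho 0.5 |
|---|---|---|---|---|---|
| 1 (plan) | 5 days to 117 years | 7.7/5.3/4.2 | 17.9/10.5/7.7 | 8/10/12% | 11/16/20% |
| 0.5 (assumed) | 49 days to 12.3 years | 2.8/2.3/2.1 | 4.2/3.3/2.8 | 18/27/35% | 32/47/60% |
| 0.3 (assumed) | 121 days to 5.0 years | 1.84/1.65/1.54 | 2.4/2.0/1.8 | 41/60/74% | 69/88/96% |

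**The case against.** Much of the case on the other side stands, and it limits the point.

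- **The tail depends on log-normality, which the plan never states.** An SD alone fixes no tail. For example, 30% of waits at 5 days, 40% at 469 days and 30% at 5 years give a median of 469 days and an SD of about 1.05, with nothing above 5 years. That pattern is contrived, but a reader who infers that SD 1 is impossible goes further than the documents allow.
- **The benchmark is for kidney only and comes from another population.** The reference list shows that the cited study concerned HCV-positive recipients, whereas this trial enrolls HCV-negative ones. A reader might extend the criticism to liver, but the documents contain no liver wait time against which SD 1 could be judged.
- **Too large an SD is conservative on the log scale.** One might infer that the plan overstates its power. On the ratio scale, a smaller SD gives narrower intervals and smaller detectable ratios. The overstatement of precision comes from the word days.
- **Zero correlation is one scenario.** Pairs are matched on center, blood type, gender and MELD or KDPI, so some positive correlation is reasonable. The table shows that it matters.
- **The endpoint is exploratory.** The synopsis says the pilot is too small for hypothesis testing, and the SD did not set the sample size. This lowers the stakes. But wait time is one of three stated objectives, and the plan chose to publish alpha, power and detectable differences for it, so those figures should be right.

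**Conclusion.** The point holds in a limited form. The log10 half-widths follow correctly from the assumed SD, so the fault lies in the input and in the back-transformation. The SD of 1 is unsourced for both organs. It is implausible for kidney if waits are roughly log-normal around a median near 469 days; for liver it is unsupported and no more can be said. Independently of the SD, 8/5/4 and 20/10/8 are fold ratios mislabelled as days.

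As planned, the comparison detects only roughly 8- to 18-fold differences and has about 8 to 12% power for the one contrast the protocol cites. With smaller assumed SDs and positive correlation, power for that contrast runs from 18% (SD 0.5, rho 0, 10 pairs) to 96% (SD 0.3, rho 0.5, 20 pairs). The documents do not show which case applies, so the reader cannot tell whether the comparison is informative. The correction is worth making, but it does not touch the primary endpoint.

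**What to change.** Rewrite the planning text in the Exploratory Endpoint section:

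- Express half-widths and detectable differences as ratios of geometric mean waits, and remove the figures in days.
- Replace the single SD with separate kidney and liver SDs estimated from the participating centers' existing wait-list records.
- State the SD of the paired log difference, or the within-pair correlation assumed.
- Show results over a range of SDs and correlations, including power for a 1.8-fold difference at 10 to 20 pairs.

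The cost is one query of existing center data and a rewrite of this planning text. Sample size, visits and data collection do not change.

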Objective #3: To compare the observed waiting time for transplant for HCV negative liver and/or kidney transplant recipients with HCV nucleic acid test (NAT) positive donors to the expected waiting time for transplant with HCV negative donors in participating regions.

Hypothesis: Receiving a NAT positive liver and/or kidney substantially shortens the wait time for liver and/or kidney transplant.

STUDY DESIGN

Description

This is a prospective multicenter, open-label, proof of concept study being conducted at up to 6 American sites (See Appendix 2). The study aims to enroll up to 30 study subjects undergoing liver and/or kidney transplantation, at least 10 of them undergoing liver transplant and at least 10 undergoing kidney transplant.

Potential study candidates will be identified through the active wait-list for liver or kidney transplant at each participating institution. The informed consent process for this trial is comprised of three steps:

1) Pre-screening: As part of pre-transplant evaluation, treating nephrologists and hepatologists will have a detailed discussion with their patients regarding high-risk donors, including those who are HCV NAT-positive. For HCV negative patients who express interest in receiving an HCV NAT-positive donor, their treating hepatologist or nephrologist will refer them to the principal investigator or co-investigator for this study.

2. Informed consent: the principal investigator, or co-investigator, will review the potential risks and benefits of participating in this trial, including a discussion regarding HCV treatment and complications of unsuccessfully treated post-transplantation HCV, including graft loss, fibrosing cholestatic hepatitis, cirrhosis and death. The discussion will also describe that organ donors in the trial might be classified as Public Health Service elevated risk for window infection with HIV. This step of the informed consent process will include documentation that each of these elements has been reviewed with the patient who understands and has ample opportunity to have all of their questions and concerns addressed. Participants who are deemed eligible and sign consent will be rendered eligible for HCV-viremic kidney or liver offers through an opt-in mechanism in the allocation system administered by the Organ Procurement and Transplantation Network/United Network for Organ Sharing (OPTN/UNOS).

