For AEs associated with laboratory abnormalities, the event should be graded on the clinical severity in the context of the underlying conditions. All AEs, regardless of cause or relationship, must be collected and reported in the eCRF database as instructed.

SAEs will be collected for the duration of the study. SAEs related to study drug, graft loss, or death will be reported to the lead investigators and the independent data and safety monitor within 24 hours of recognition by study staff. Stable chronic conditions that are present prior to the Pre-Transplant Day and do not worsen during the treatment period and safety follow up period are not considered adverse events.

Safety Review. When the first 10 study subjects reach treatment week 4, the lead investigators and the independent data and safety monitor will conduct a safety and efficacy review. When these subjects reach follow up week 12 (24 weeks after starting study drug), the lead investigators and the independent data and safety monitor will conduct another safety and efficacy review.

Early termination: Participants may withdraw their consent to participate in this study at any time after they sign informed consent. Principal investigators can terminate participant(s) from the study for safety concerns. Subjects who take at least one dose of study drug and do not complete the planned 12 weeks of treatment will come for an early end of treatment visit.

STATISTICAL CONSIDERATIONS

Analysis Objectives

The primary objective of this study is to determine the efficacy of SOF/VEL in viral eradication among HCV negative liver and/or kidney transplant recipients with HCV NAT positive donors.

The secondary objective of this study is to determine the safety and tolerability of all SOF/VEL among HCV negative liver and/or kidney transplant recipients with HCV NAT positive donors.

The exploratory objective of this study is to compare the observed waiting time for transplant for HCV negative liver and/or kidney transplant recipients with HCV NAT positive donors to the expected waiting time for transplant with HCV negative donors at the participating centers.

Primary Efficacy Endpoint

The proportion of participants with SVR 12 defined as HCV RNA < lower limit of quantification 12 weeks after last dose of antiviral therapy.

Secondary Endpoints:

- Proportion of subjects with SVR24 defined as HCV RNA < lower limit of quantification 24 weeks after last dose of antiviral therapy;

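### The wait-time half-widths of 8, 5 and 4 days are antilogs of log10 half-widths, so they are multiplicative factors, not days; the paired-test figures of 20, 10 and 8 days are very probably the same slip, and the paired SD or correlation behind them is not stated

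*Combined protocol and SAP*

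**What the plan says.** Objective #3 concerns waiting time and carries its own hypothesis: "Receiving a NAT positive liver and/or kidney substantially shortens the wait time for liver and/or kidney transplant". Analysis Objectives classes it as exploratory: "The exploratory objective of this study is to compare the observed waiting time for transplant".

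The Exploratory Endpoint text under Efficacy Analysis sets the scale: "mean wait time in log₁₀ days will be calculated separately for liver and kidney transplant recipients". With an SD of 1 log10 day and 10, 15 or 20 recipients per organ type, it says "we have 80% power to obtain a two-sided 95% CI half-width of 8, 5, and 4 days, respectively", and in the same sentence gives these as "CI half-width of 0.9, 0.7, and 0.6" on the log10 scale.

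The next paragraph matches each recipient of an HCV positive organ to the next suitable recipient of an HCV negative organ at the same centre. Mean log10 days are compared separately for liver and kidney. The plan expects the following data: "We anticipate obtaining wait time on 60 transplant recipients (at least 20 liver and 20 kidney recipients"). The power statement rests on a two-sided paired t-test at alpha 0.05 and reads "we estimate having 80% power to detect a mean difference in wait time of 20, 10, and 8 days". The three differences are attached, in that order, to the following numbers: "for sample sizes of 20, 30, and 40 patients, respectively". It prints no log10 values for these three differences, and no SD of paired differences or within-pair correlation.

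The Background cites median kidney waits of 469 days for HCV positive and 856 days for HCV negative organs. These are not used as design assumptions.

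**The concern.** A half-width on the log10 scale is a difference of logarithms. Its antilog is a ratio and has no unit. To express it in days one needs a reference wait, and the calculation uses none.

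As worded, the study appears able to place the mean wait within 4 to 8 days and to detect differences of 8 to 20 days. The plan's own SD supports precision only to within a several-fold factor. A reader relying on the figures in days could take an inconclusive comparison as evidence that acceptance of an HCV positive organ makes no useful difference to the wait, when the comparison could detect only very large ratios.

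**Working it through.** **Inputs.** From the Exploratory Endpoint text: SD 1 log10 day in a single group; n = 10, 15, 20; 95% two-sided interval; 80% probability; paired t-test with two-sided alpha 0.05; 20, 30 and 40 patients, read as 10, 15 and 20 pairs. From the Background: 469 and 856 days. The within-pair correlation r is not in the documents and is varied below as an assumption.

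**1. Reproducing 8, 5 and 4.** 10^0.9 = 7.94, 10^0.7 = 5.01, 10^0.6 = 3.98. They round to the printed figures, so these are antilogs.

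**2. What the printed half-widths mean.** The interval runs from GM / 10^h to GM × 10^h, where GM is the geometric mean. With GM = 469 days for illustration:

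| n | h (log10) | 95% CI, days | If read as days |
|---|---|---|---|
| 10 | 0.9 | 59 to 3725 | 461 to 477 |
| 15 | 0.7 | 94 to 2351 | 464 to 474 |
| 20 | 0.6 | 118 to 1867 | 465 to 473 |

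**3. Where 0.9, 0.7 and 0.6 come from.** The normal detectable-difference formula (z.975 + z.80) × SD / √n, with 1.960 + 0.842 = 2.802 and SD 1, gives 0.886, 0.723 and 0.626. These round to 0.9, 0.7 and 0.6. A half-width met with 80% probability is t(.975, n−1) × √[χ²(.80, n−1)/(n−1)] / √n:

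- n = 10: 2.262 × √(12.242/9) / √10 = 0.834, factor 6.83
- n = 15: 2.145 × √(18.151/14) / √15 = 0.631, factor 4.27
- n = 20: 2.093 × √(23.900/19) / √20 = 0.525, factor 3.35

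The printed values thus look like detectable differences labelled as half-widths. They are conservative in that role: the probability that the half-width is no larger than printed is 0.89, 0.93 and 0.96.

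**4. The paired figures as antilogs.** Take SD 1 per group and r = 0, so that the SD of differences is √2. Then 2.802 × √2 / √pairs gives 1.253, 1.023 and 0.886 for 10, 15 and 20 pairs. Rounded to one decimal these are 1.3, 1.0 and 0.9, with antilogs 19.95, 10.0 and 7.94, which are the printed 20, 10 and 8.

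**5. The paired figures as literal days.** The exact paired t-test with 80% power detects 0.996, 0.778 and 0.660 SDs of the differences at 10, 15 and 20 pairs. The SD in days would have to be 20/0.996 = 20.1, 10/0.778 = 12.9 and 8/0.660 = 12.1. No single SD fits, and allowing for rounding to whole days does not help (19.6 to 20.6, 12.2 to 13.5, 11.4 to 12.9). If 20, 30 and 40 are read as pairs, the SDs needed are 30.3, 18.9 and 17.6 days, again not one value.

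**6. Detectable ratios of geometric means.** Exact paired t-test, SD 1 per group, SD of differences = √[2(1−r)]:

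| r (assumed) | 10 pairs | 15 pairs | 20 pairs |
|---|---|---|---|
| 0 | 25.6 | 12.6 | 8.6 |
| 0.5 | 9.9 | 6.0 | 4.6 |

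For scale, the Background medians differ by a factor of 856/469 = 1.83 (0.26 log10). At 20 pairs, power for that ratio is about 12% at r = 0 and 20% at r = 0.5.

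**The case against.** The endpoint is exploratory, the synopsis says the pilot is too small for hypothesis testing, and no sample size depends on these figures. The log10 half-widths stand beside the days, and the analysis scale is properly specified, so the eventual estimate will not be wrong. All of this stands, and it limits the weight of the point. It does not make the figures in days correct: for waiting time the plan does name a test, an alpha level and a power, and nothing elsewhere describes these figures as ratios.

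Three stronger readings are tempting, and the documents do not support them.

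- A reader might infer that the log10 half-widths are themselves too small. They are not: they exceed the 80% assurance values, so the 80% statement holds. The doubtful part is the label, since they match a detectable-difference formula.
- A reader might treat the paired figures as proven antilogs. No log10 values are printed for them, so this remains an inference, though a strong one.
- A reader might try to recover the paired SD from the printed figures. It is not identifiable. The exact t-test fits an SD of about 1.29 to 1.35 log10; the normal formula fits √2 with 10, 15 and 20 pairs, or 2 if the sample sizes are read as pairs. If the stated SD of 1 per group was carried over, what is missing may be only the correlation. Either way, the plan does not say.

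**Conclusion.** The unit is wrong for the confidence-interval figures. This is certain, because both sets of numbers are printed: 8, 5 and 4 are factors around the geometric mean. That 20, 10 and 8 are ratios of geometric means is very probable. It rests on the log10 comparison scale, on the exact match under SD 1 per group with zero correlation, and on the failure of any single SD in days.

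The omission of the paired SD or correlation is a separate, real gap. Between correlations of 0 and 0.5, the detectable ratio at 20 pairs moves from 8.6 to 4.6. The 469-day illustration assumes that a cited kidney median can stand in for a geometric mean, and it says nothing about liver.

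The overstatement is large but confined to the stated precision and power of one exploratory endpoint. It should be corrected; it does not threaten the trial's main conclusions.

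**What to change.** Delete every figure in days from the precision and power statements, and use one set of numbers for the interval. Either:

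- say that, with at least 80% probability, the 95% CI extends no further than a factor of 6.9, 4.3 and 3.4 either side of the geometric mean for n = 10, 15 and 20 (the 80% assurance values rounded up); or
- keep 0.9, 0.7 and 0.6 log10 and call them factors of 8, 5 and 4, described as conservative bounds.

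Do not mix the two, because they come from different calculations.

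For the matched comparison, state the number of pairs and the assumed SD of paired log10 differences (or the correlation) with its source. Give the detectable ratio of geometric means from the exact paired t-test; the second table in the working supplies reference values. Report the observed comparison as a ratio of geometric means with its 95% CI.

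The cost is rewording and a short recalculation, with no change to enrolment, data collection or the primary analysis. The downside is that the stated precision and power become visibly less favourable.
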